4.6 Interim Analysis

N/A

5 STUDY INTERVENTION (DEVICE, DRUG, OR OTHER INTERVENTION)

See section 3.2 for further intervention details. No device or drug studied.

6 STUDY INTERVENTION ADMINISTRATION (IF APPLICABLE)

Blinding and randomization procedures already explained in sections 2.1, 3.1, and 3.2

7. SAFETY MANAGEMENT

Given the low potential for risk of harm to participants, the data safety monitoring (DSM) plan emphasizes close monitoring of the trial by the principal investigator, project manager, onsite manager, study statistician, and a DSM officer. This DSM team will regularly review subject accrual, adherence to study protocols, dropouts, adverse events, and participant confidentiality. Specifically, the principal investigator and project manager will meet on a biweekly basis throughout all phases of the project to review the study progress and any concerns about quality control and/or participant safety. Additionally, they will review progress with the DSM officer quarterly and within two weeks when adverse events occur. Prior to subject engagement, the full DSM team will meet in person to review study protocols (e.g., recruitment, consent, adverse events monitoring), finalize the DSM plan, and establish a template for quarterly reporting. During active subject engagement, the onsite manager and Kentucky-based co-investigator will participate in biweekly meetings with the principal investigator and project manager. The project manager will also work with the study statistician to prepare reports for the DSM officer on participant accrual, adherence, and withdrawal/dropouts based on the approved reporting template. The DSM officer will be asked to review and approve these reports. In addition to these quarterly reports, any adverse events or concerns regarding confidentiality will be reviewed by the DSM officer within two weeks of the event. We do not anticipate the need for interim analyses for early termination due to intervention effectiveness or futility. We feel that this level of monitoring is commensurate with the risks and complexity of the proposed study.

Measurement and Reporting of Adverse Events

At enrollment, we will inform center staff and TA providers to contact the project manager if they feel an injury or illness may have occurred to them or a child in their care as a result of their participation in this study. If such an event occurs, the project manager will collect a detailed description of the event, the adverse outcome, severity of the adverse event, and whether or not participants viewed it as related to the study. This report will then be reviewed by the DSM officer, who will categorize it as: *definitely*

unrelated, or unlikely, possibly, probably, or definitely related to study participation. Although some injuries may be anticipated as a result of an intervention that promotes regular physical activity for children, in our previous center-based work, no injuries related to participation occurred. We therefore anticipate that injury risk is present, but minimal. Adverse event reports will be submitted to the IRB after they are completed by the DSM officer. A summary of these reports will be submitted to the NIH project officer on an annual basis as needed.

Participant Confidentiality

This study will collect provider and organizational-level measures. Collection of data is for research purposes only and is kept in strict confidence by study personnel. Data collection forms and contact information used to implement the intervention will be kept in locked file cabinets in the UNC-Chapel Hill study offices. Online data collection will occur through Qualtrics and is password protected. Participants will be assigned an ID number which will be used to minimize the use of names on forms. Any forms linking participant ID and name will be stored separately, away from other survey data. Electronic data files will be stored on a secure, password protected server. Except when required by law, participants will not be identified by name, address, telephone number, or any other direct personal identifier in study records disclosed outside of UNC-Chapel Hill. Written informed consent will be obtained using a UNC approved consent form.

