Test Article(s) (If Applicable)	
TA Coaches are randomized to provide Basic Go NAPSACC or Enhanced Go NAPSACC delivery to their enrolled centers.
 
In Basic Go NAPSACC (general prescription) TA Coaches will:
 
• invite their centers to register, complete self-assessments, and create action plans• encourage centers to complete 2 cycles of Go NAPSACC’s 5-step improvement process• check in monthly to evaluate progress, provide suggestions, and trouble shoot issues. 
In Enhanced Go NAPSACC TA Coaches will:
 
• Help center create an implementation team, conduct a readiness assessment, and guide choice of a priority challenge for each center.• Invite centers to register and complete self-assessments.• Help director create an implementation plan for the improvement process. This plan will be tailored based on the priority challenge identified from readiness assessment.• Check in monthly to evaluate progress, provide suggestions, and trouble shoot issues.• Facilitate quarterly cross-center meetings to create community and discuss issues.• Participate in a group check-in with a Go NAPSACC advisor (UNC research team) monthly and talk with UNC team individually each quarter.

Study Design	This is a type 3 hybrid effectiveness-implementation RCT with a clustered parallel group intervention design. TA coaches were randomized to deliver Basic Go NAPSACC or Enhanced Go NAPSACC to their enrolled centers.
Subject Population Key criteria for Inclusion and Exclusion:	
For this study we will recruit Technical Assistants (TA Coaches) and child care centers. From each center, we will recruit and enroll a director and 2 teachers.
 
TA Coaches
 
 • Must either be Quality coach or a Healthy and Safety coach • Must be able to read and speak English 
Child Care Centers
 
 • Must be part of a participating TA coach's current caseload • Have no plans to close in the coming year • Have at least one classroom serving preschool children • Serve at least lunch to the children • Not serve special needs children exclusively 
Child Care Providers
 
 • Teacher must be the lead teacher in a preschool classroom • Center directors and teachers must be able to read and speak English

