Number Of Subjects	
TA Coaches: BL n = 27; FU n = 26
 
Child Care Centers: BL n = 97; FU n = 88
 
Child Care Providers: BL n = 257; FU old n = 139, FU new n = 82

Study Duration	Each subject's participation will last approximately 14 months; 1 month for baseline data collection, 12 months of intervention, and 1 month of follow up data collection. The entire study is expected to last approximately 3 ½ years.
Study Phases	
(1) Screening and recruitment: During this phase we will identify and recruit TA coaches and get lists of the centers they serve. Centers will be screened for eligibility and recruited randomly. After a director and teachers consent, baseline data collection will be completed (2) Intervention: After baseline measurement, TAs will be randomly assigned to Basic or Enhanced Go NAPSACC implementation and the 12-month intervention will proceed (3) Follow-Up: After the 12-month intervention, follow up measures and process evaluations will be completed.

Efficacy Evaluations	
 • Primary Objective 
 ○ Aim 1. Compare intervention impact on implementation of healthy weight practices. 
 ▪ EPAO-SR Nutrition and Physical activity environment scores. • Secondary Objectives 
 ○ Aim 2. Evaluate adoption, implementation, and maintenance by group. 
 ▪ Percent of centers creating accounts, completing self-assessments, selecting goals, and creation of action plans will be captured by the Go NAPSACC website and extracted using the registration and detailed activity reports. ○ Aim 3. Examine how organizational factors predict implementation. 
 ▪ Surveys completed by directors, teachers, and TA coaches. ▪ Fernandez's CFIR Inner Setting: Culture, Culture Stress, Culture Effort, Implementation Climate, Leadership Engagement, and Available Resources. ▪ TCU's Organizational Readiness for Change: Networks and Communications and Access to Knowledge and Information. ○ Aim 4. Calculate incremental cost-effectiveness ratio for environment change. 
 ▪ Costs include TA coaches time and any resources required to train and support centers for 12 months. Costs will be tracked in the TA Activity and

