2.3 Study Duration, Enrollment and Number of Subjects

Study duration varies by participant type. TA coaches will be involved for approximately 18 months, center directors for approximately 16 months, and teachers for approximately 4 weeks.

The goal is to enroll 97 centers, a director and at least 1 teacher at each center. When possible, we will recruit 2 teachers who work with children 3-5 years old at each center. We will enroll 8 TA coaches across the 8 regions of Kentucky through Child Care Aware of Kentucky (Northern Bluegrass, Southern Bluegrass, Salt River Trail, Eastern Mountain, Cumberland, Two Rivers, Jefferson, and The Lakes). This will be done across 4 waves.

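### Adverse events are captured only by spontaneous, suspicion-based reports, with no described question about injuries during the 12 intervention months or at follow-up, so a zero count could not be read as absence of injuries

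*Combined protocol and SAP*

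**What the plan says.** Section 7 (Safety Management, Measurement and Reporting of Adverse Events) sets the timing of the instruction: "At enrollment, we will inform center staff and TA providers". The instruction itself is that they should "contact the project manager if they feel an injury or illness may have occurred to them or a child in their care as a result" (that is, of participating). Once such a contact is made, the project manager records what happened, the outcome, the severity, and "whether or not participants viewed it as related to the study". The DSM officer then grades causality on a scale that runs from definitely "unrelated, or unlikely, possibly, probably, or definitely related to study participation".

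The same section accepts that "some injuries may be anticipated as a result of an intervention that promotes regular physical activity for children". It calls the risk minimal because no participation-related injuries occurred in the team's earlier center-based work.

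The contacts that could carry a question about injuries are these:

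- **Coach contacts.** In both arms, the synopsis (Test Article(s)) has coaches "check in monthly to evaluate progress, provide suggestions, and trouble shoot issues". Coaches log their activities in the TA Activity Log.
- **Follow-up surveys.** Sections 3.3 and 4 repeat the baseline measures and add process-evaluation questions, including delivery and cost.
- **Safety evaluations.** The synopsis and section 4.3 give these as not applicable.

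On who is present and for how long, section 2.3 states: "TA coaches will be involved for approximately 18 months, center directors for approximately 16 months, and teachers for approximately 4 weeks". The synopsis (Number Of Subjects) lists 257 child care providers at baseline and, at follow-up, "FU old n = 139, FU new n = 82".

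**The concern.** The reporter's suspicion comes before the expert's judgment. The plan gives relatedness to the DSM officer and provides a category for events that are definitely unrelated, yet staff are not asked to send in events that they think unrelated. A fall during active play that a center added under its action plan can look like an ordinary fall. If the teacher sees it that way, the officer never gets to grade it.

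The described instruction is also tied to enrollment, while staff turn over during the 12 months. Someone who joins a center midway has no described point at which the study tells them what to report.

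Two things are at stake. A center with a real problem might not be recognized while the intervention is running. And a count of zero or near zero could be carried forward as reassurance, as section 7 already does with the count from earlier work.

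**Working it through.** The plan states no injury rate, number of children or safety power, so there is no figure to reproduce. The check has three parts.

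**1. Is any contact described as asking about injuries?** The monthly check-ins cover progress, suggestions and troubleshooting. The activity log records implementation activities. The follow-up additions are process evaluation. The interviews concern experience with the program. The DSM team's biweekly and quarterly reviews, and the two-week review of events, act on what has already been reported. Number of described contacts that ask about injuries: 0.

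**2. How far does an instruction at enrollment reach?** Inputs are from the synopsis, Number Of Subjects; I take the follow-up count labelled old to be baseline providers.

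- Baseline providers counted at follow-up: 139/257 = 54%.
- Baseline providers not counted at follow-up: 257 − 139 = 118, and 118/257 = 46%. Some belong to the 97 − 88 = 9 centers without follow-up, and some may still have been at work but not surveyed.
- New providers among those at follow-up: 82/(139 + 82) = 82/221 = 37%.

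Section 3.3 applies the baseline procedures again after 12 months, so a provider first enrolled then would get the study's instruction after the intervention. The synopsis does not say when the 82 joined their centers.

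**3. What would a zero count show?** Let p be the true 12-month risk that a center has at least one related injury, and c the chance that such a center produces a report. Both are assumptions, and centers are treated as independent. With zero reports from n centers, the one-sided 95% upper bound on p is [1 − 0.05^(1/n)]/c. For n = 97 and c = 1 this is 3.0% (for n = 88, 3.3%). The chance of zero reports is (1 − p·c)^97.

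| Assumed c | Upper bound on p, n = 97 | P(zero reports), p = 2% | p = 5% | p = 10% |
|---|---|---|---|---|
| 100% | 3.0% | 14.1% | 0.7% | 0.0% |
| 50% | 6.1% | 37.7% | 8.6% | 0.7% |
| 25% | 12.2% | 61.5% | 29.5% | 8.6% |
| 10% | 30.4% | 82.3% | 61.5% | 37.7% |

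At a true risk of 5% per center, zero reports would be very unlikely with full reporting and more likely than not at 10% reporting. The documents give no basis for choosing a row.

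**The case against.** The best case for the plan is proportionality. The study is minimal risk, both arms use the same program, the measures are at provider and organization level, and no safety objective or between-arm safety comparison is planned. Even a complete count would not isolate the program's injury risk, because there is no arm without the program. Section 7 also has the DSM team settle its plan before subjects are engaged, so operational detail may sit there, and the consent pages are not available to check. All of this stands. It limits the weight of the point, but it does not remove the filter that section 7 itself states.

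A reader might infer more than the documents support:

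- **That only events staff already blame on the study are reported.** The wording asks for events that may have resulted from participation. That is a threshold of suspicion, not of firm attribution.
- **That staff are told only once.** The text places the instruction at enrollment and is silent on reminders. A single notice is an inference.
- **That teachers have no part in the 12 months.** Section 2.3 gives about 4 weeks, but the synopsis gives about 14 months for each subject, and Enhanced implementation teams include at least two staff with check-ins and cross-center meetings. Directors and coaches are also covered by the instruction and stay throughout.
- **That the follow-up surveys contain no safety item.** The process questions are not listed in full. It can be said only that none is described.

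**Conclusion.** The point holds as a gap in ascertainment. Reporting is spontaneous and passes through the reporter's own suspicion, the instruction is described only at enrollment, and no contact is described as asking about injuries. Injuries that staff do not link to the study may be missed; it does not follow that they will be, since staff can report at any time and reported events are reviewed within two weeks.

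The measurable part is that 82 of 221 follow-up providers (37%) are new and may have had no study instruction during the intervention. A reader might conclude that a zero count would mean nothing. That goes too far: it would be weak evidence, with a bound that moves from 3.0% to 30.4% per center as assumed reporting falls from 100% to 10%. It could not be read as absence of injuries. Nor could it support a comparison of arms, because the Enhanced teams and meetings could make spontaneous reporting differ by arm.

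The primary analysis is unaffected. This is a cheap improvement. The percentages in the table rest on assumed p and c; the turnover figures rest on the synopsis counts alone.

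**What to change.** In section 7, ask staff and coaches to report any child or staff injury that occurred during an activity introduced or changed under a Go NAPSACC action plan and needed medical attention, whatever they think caused it. The DSM officer assigns relatedness. Do not widen this to every illness needing medical attention, which would send unrelated illness to DSM and IRB review.

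Add one identical yes/no item on this to the monthly coach check-in in both arms, recorded in the existing TA Activity Log, and one retrospective item to the 12-month director and teacher surveys. Keep it to contacts that both arms have, so that Enhanced's extra meetings do not raise its detection.

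The cost is one reworded sentence, one log field and one survey item, with no new staff or visits. Some ordinary play injuries will be reported and graded unrelated, which adds a little work for the DSM officer and the IRB, and staff must know which activities the action plan changed.

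The synopsis already shows follow-up counts, so prompts during the intervention may no longer be possible. In that case, state in section 7 and in any report that adverse events are spontaneous reports only and that a zero count is not a safety finding.

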8. DATA COLLECTION AND MANAGEMENT

Due to study modifications associated with COVID 19 data collection utilized remote collection methods including phone calls, online surveys, and video conferencing. All methods and modifications were approved by the UNC IRB and funding officers. Data completion and quality was monitored by the project manager and data manager during this transition and throughout baseline and follow-up assessments. All data are housed on secure university servers with direct access limited to relevant research personnel (PI, statistician, project and data managers). De-identified data will be housed for long term access using the UNC data storage system. A more complete description of the important and maintenance of participant confidentiality can be found in section 7 (above).

9. RECRUITMENT STRATEGY

The 97 centers will be recruited over 4 waves from the 11 regions that span the state. We will work with Child Care Aware Kentucky and identify Technical Assistants in each region. We will then identify all licensed child care centers that each TA works with and randomly select a sample of 25 centers for each TA to target for recruitment. TA providers will help distribute recruitment materials (provided by the project) to the child care centers and gauge initial their interest. The names and contact information from interested centers will be supplied to the project team for follow-up. Trained research assistants will follow up with interested centers by telephone to review study details, confirm eligibility, and verify interest of the center. Once participation is confirmed, two 3-5 year old classroom teachers will be chosen to be recruited. A follow up email with information to go over with potential teachers. Then those teachers would be called at the center and recruited by phone to review study materials and confirm interest.

10. CONSENT PROCESS

Once providers have been explained the study over the phone and eligibility and interest is confirmed consent will be collected online via a Qualtrics link that is sent through a study email by a study staff member. A downloadable link will be included in the Qualtrics and a blank copy of the consent form will be attached to the email. Participants can take as much time as they would like to look over the consent form and ask questions before signing online or on paper. If paper is requested a postage provided envelope will be provided to mail back their signed consent form. These paper copies will be kept away from other data in locked cabinets only accessible by study staff.

11. PLANS FOR PUBLICATION

Study results and additional findings with published in 2-3 manuscripts submitted to peer reviewed journals. A protocol paper has been published.

APPENDIX

Table 2 Measurement of implementation context

CFIR construct	Source	Asked to:	
		Directors and teachers	Coaches
Networks and communications	ORC: Organizational Climate–Communication [41, 42]	Yes	No
Culture	ISS: Culture, Culture Stress, Culture Effort [40]	Yes	No
Implementation climate	ISS: Implementation Climate [40]	Yes	Yes
Readiness for implementation			
Leadership engagement	ISS: Leadership Engagement [40]	Yes	No
Available resources	ISS: Available resources [40]	Yes	Yes
Access to information and knowledge	ORC: Resources–Training [41, 42]	Yes	Yes
Knowledge and beliefs about intervention			
	TDFQ: Knowledge [43–45]	Yes	Yes
	TDFQ: Beliefs and Consequences [43–45]	Yes	Yes
Self-efficacy	TDFQ: Beliefs about Capabilities [43–45]	Yes	Yes
